### 3.5.1. General introduction

#### 3.5.1.1. Applicable, Law, guidance and standards

This document has been written in accordance with the **EU MDR** and is compliant with the **ISO 14155 standard for Clinical investigation of medical devices for human subjects — Good clinical practice** and ISO 14791 Risk Management

Additionally the MDCG (2020-1) Guidance on clinical evaluation (MDR) / Performance evaluation (IVDR) of medical device software is used.

#### 3.5.1.2. Summary of the project

##### Aim

This study is set-up as a pre-market clinical investigation of a non-CE marked medical device. The main goal of the study is to measure the efficacy of the ALICE app (Assistant for Listening and Communication Enhancement), a newly developed software application that will function as an added service in the aural rehabilitation of persons with HI, by providing remote monitoring, training and follow-up.

##### Medical device & classification

The software application is considered to be a medical device type IIa, because it is an active device that monitors a persons' hearing disability and provides a personalized rehabilitation program to alleviate (some of) the experienced hearing difficulties (and could be used to take decisions with a therapeutic purpose of low risk impact, which falls under rule 11 of the MDR).

#### 3.5.1.3. Background

Hearing impairment (HI) is listed as one of the most common health problems in the world and one of the largest sources of years lived with disability (WHO, 2021). More than 5% of the world population has disabling HI, about 466 million people worldwide (WHO, 2021). HI places a burden on human health, society and healthcare expenditure. Without appropriate follow-up, a person with HI will experience difficulties with communication, learning, social-emotional functioning, employment and quality of life (Davis et al. 2016). Moreover, HI has been related to cognitive decline and is also a potentially modifiable risk factor for dementia (Livingston et al., 2020).

To overcome the risks and difficulties associated with HI, different rehabilitation and treatments option exist. The overarching term for the treatment of persons with HI is called **Aural rehabilitation (AR)**. AR consists of 4 cornerstones (Boothroyd, 2007):

- Sensory management (hearing aids, cochlear implants, assistive listening devices...) to enhance auditory function;
- Knowledge and skills (to improve the outcome);
- Perceptual training;
- Counselling (motivational engagement).

This multidisciplinary and holistic approach is recommended as best practice in hearing health care, but not all persons with HI have access to these four cornerstones.

- ⇒ Adults with severe to profound HI receive the four different cornerstones of AR at rehabilitation centers for a defined period of time. This defined period encompasses only a few years. After this initial treatment period, adults are not reimbursed for further follow-up at rehabilitation centers and have to find multidisciplinary follow-up elsewhere. Moreover,

due to the limited capacity at rehabilitation centers, many persons end up on waiting lists and lose their motivation to manage their HI.

- ⇒ Adults with mild to moderate HI are often referred to hearing aid centers, where rehabilitation is mainly focused on sensory management (technological solutions, such as hearing aids and assistive listening devices). However, the uptake of hearing technology remains low, with an adoption rate of only 20-40% of those who seek help (Abrams & Kihm, 2015; Laureyns et al. 2015; Hougaard et al., 2016; van Leeuwen et al., 2021). Hearing aids manage sensory loss, but do not restore hearing to normal (Davis et al. 2016). As a result, low satisfaction is reported in challenging listening situations, such as understanding speech in noise or over a distance.
- ⇒ Adults with perceived hearing difficulties, without diagnosed HI do not receive any AR.

In summary, many persons with HI do not receive optimal treatment at the right time, due to many barriers and difficulties in the standard hearing health care. These difficulties and barriers are mostly related to time constrictions, lack of knowledge and limited reimbursement.

Adherence and uptake of hearing aid technology could be higher with additional AR services (low-friction; easy to access), which would also alleviate the current rehabilitation centers.

Ideally, AR could be provided through a remote online application that provides perceptual training, counselling and additional information, in order to enhance the listening and communication strategies of persons with perceived hearing difficulties.

### Previous research with LUISTER (S59845)

During a previous study, ExpORL developed the LUISTER app (“Leuven Interactief Schema voor gehoorTraining, Evaluatie en gehoorRevalidatie”; EC number: S59845).

The LUISTER programme consists of different tests to evaluate listening and communication skills (the validated digit triplet test and the phoneme discrimination test) and more than 500 automated training tasks on a tablet ([name] et al., 2021 and Magits et al., 2023). The LUISTER app was developed and validated with adults with a profound HI and a cochlear implant (Magits et al., 2023). The results of this study provided the scientific evidence for the added benefit of the LUISTER training for persons with HI.

LUISTER was an important first start to greater accessibility, interactivity, and personalisation of hearing care, which can lead to improvements in self-management of HI, at home whenever convenient. However, LUISTER still depended on a hearing care professional (HCP) informing a client on what to do next. This is partly because the results of the training paradigm are not self-explanatory and partly due to a lack of guidance and counselling offered in the programme. In addition, the HCP cannot serve multiple clients simultaneously with LUISTER.

Therefore, LUISTER was further developed into an optimized app called ALICE (Assistant for Listening and Communication Enhancement), containing a closed loop system and additional features to address the aforementioned gaps.

## 3.5.2. Identification and description of the investigational device

### 3.5.2.1. Description of the investigational device

See IB for a more detailed description.

#### ALICE

The ALICE app consists of two software units:

- The *ALICE-Client* app for persons with HI or listening difficulties. The app provides remote monitoring, training and counselling.

- The *ALICE-Pro* dashboard for hearing care practitioners (HCP) involved in the aural rehabilitation process of persons with HI or persons with listening difficulties. ALICE-Pro provides the audiologists with data and analytics of their clients.

[figure not shown]

Figure 1. Overview of ALICE-Pro (left) and ALICE-Client (right) including the incorporation of the existing (and validated) LUISTER app

#### ALICE-Client

The ALICE-Client app can be downloaded onto the client's personal smart device (smartphone or tablet). Similar to LUISTER, the app contains different monitoring tasks and a large number of listening training exercises. For the ALICE app a counselling module was added (see below).

- The **monitoring tests**, (cfr. LUISTER app) consist of the validated digit triplet test (DTT) and the phoneme discrimination test. Both are speech perception tests: the DTT is used to monitor the level of speech understanding in noise, the phoneme discrimination test determines how well a person can discriminate between different phonemes. The outcome of the DTT determines the starting level of the first speech in noise exercise. The outcome of the phoneme discrimination test determines which phoneme exercises will be trained first.
- The **listening training exercises** (cfr. LUISTER app) consist of a range of auditory-cognitive tasks. Five types of listening training exercises are available: vowels, consonants, exercises according to a theme, recognition of voices and emphasis, clock and cognitive sentences. Exercises are performed in quiet and in various types/levels of background noise. The client can choose their answer from a closed set of options (3-6-9). Feedback is provided in a targeted way (not only 'correct' or 'wrong', but with information on the type of errors that are made).
  - ⇒ Both monitoring tasks and training exercises have been researched (cfr. S59845) and documented in [name] et al., 2021 and Magits et al., 2023, van Wilderode et al., 2023).
- The **counselling module** consists of different questions about the clients' listening experience and difficulties. These questions are based on validated questionnaires such as the Speech Spatial and Quality of hearing questionnaire (SSQ; Gatehouse and Noble, 2004), the Hearing Handicap Inventory for Adults/the Elderly (Ventry and Weinstein, 1982) and the Fatigue Assessment Scale (De Vries et al., 2004) among others. Clients will be presented with 3

questions every other day to inventory their daily experiences. Questions can be answered on a 5-point Likert scale.

[figure not shown]

Figure 2: Screenshots of the ALICE-Client app, very similar to the LUISTER app. On top: monitoring tasks, DTT and phoneme discrimination tests. Below listening training exercises.

#### ALICE-Pro

The ALICE-Pro dashboard is accessible from a website on a dashboard computer.

[figure not shown]
ALICE-Pro allows the HCP to gain insight in the listening and communication skills of their clients based on the data and results of the client app, i.e. results of monitoring tasks, listening training exercises (Pro Portal; Figure 2) and on daily life experiences of their clients (counselling module). The output of the counselling module includes information about the clients' well-being, their degree of self-management and difficulties they encounter in daily life.

This information provides the HCP with a systematic overview of the clients' results and needs that can be used as guidance during follow-up consultations.

## Overzicht dtt

## Overzicht foneem discriminatie tests

### Medeklinkers

### Klinkers

Figure 3: screenshots of the ALICE-Pro dashboard showing one clients results, i.e.: the progress on the training tasks, the results of the digit triplet tests and the results of the phoneme discrimination tests (left: consonants, right: vowels)

### 3.5.2.2. Intended purpose of the investigational device

ALICE (Assistant for Listening and Communication enhancement) is a software application that will function as an added service in the aural rehabilitation of persons with HI, by providing remote monitoring, training and follow-up .

The software application is considered to be a medical device type IIa, because it is an active device that monitors a persons' hearing disability and provides a personalized rehabilitation program to alleviate (some of) the experienced hearing difficulties.

### 3.5.2.3. The populations and indications for which the investigational device is intended

- Population = ALICE will be used in Dutch speaking individuals, who are able to read and follow instructions on a smartphone or tablet;
- Indication and intended users = the ALICE-Client app will be used by persons with or without HI who experience listening difficulties. In the clinical study the clients will be monitored closely by their HCPs by using the ALICE-Pro dashboard (see section 3.5.6. for further details).

### 3.5.2.4. Details concerning the manufacturer of the investigational device.

The ALICE app is developed by the Research Group Experimental Oto-rhino-laryngology (ExpORL). ExpORL is part of the Department of Neurosciences of the Catholic University in Leuven (KU Leuven).

Over the years, the ExpORL research group has developed a number of products (research purpose only). These products cover the entire hearing care trajectory from screening (quickly testing a large population without detailed diagnostics), to detailed and ecologically valid diagnostics and intervention. The ALICE app is the first product that will be launched commercially as stand-alone software. The ALICE app is defined as software as a medical device (SaMD).

### 3.5.2.5. Name or number of the model/type, including software version and accessories, if any, to permit full identification.

Name	Software version
ALICE	v.0.12.0

### 3.5.2.6. Description as to how traceability shall be achieved during and after the clinical investigation, for example by assignment of lot numbers, batch numbers or serial numbers.

In accordance with Annex VI, Part C of the Medical Device Regulation (EU) 2017/745 (MDR), only software which is commercially available on its own as well as software which constitutes a device in itself shall be subject to Unique Device Identifier (UDI) requirements.

For the clinical investigation, traceability shall be achieved by restricted access to the app, only subjects who are enrolled in the study and have signed the informed consent will be granted access (see section 3.5.6. for further details on the enrolment procedure)

### 3.5.2.7. Summary of the necessary training and experience needed to use the investigational device based on risk management.

Both the ALICE-Client, as the ALICE-Pro software are developed following the applicable ISO standards, including ISO 62366 Application of Usability Engineering to Medical Devices, and are considered to be easy to use.

At the start of the clinical investigations, a workshop will be organized to provide (See in more details in onboarding procedure (3.5.4.3)):

- A general introduction about the intended use of the app,
- Information about the compatibility of the app with personal (streaming) devices,
- The safety measures that should be taken into account by both HCP and their clients:
  - Procedure to control the loudness of the stimuli provided by the app

- Procedure to follow to ensure safe data management (compliant with GDPR)
- Procedure to follow in case of adverse events and/or device malfunction

The app provides a onboarding process, to get the user familiar with the interface of the app, the intended use and its functionalities. For every functionality, clearly written instructions are provided within the app.

### 3.5.3. Justification for the design of the clinical investigation

#### 3.5.3.1. Evaluation of the results of the relevant pre-clinical testing/assessment and prior clinical investigations carried out to justify the use of the investigational device in human subjects

##### LUISTER

The monitoring and training tasks included in the ALICE app were previously evaluated by the ExpORL research group. This evaluation was performed as part of the LUISTER program in 40 persons with profound HI and a cochlear implant in a randomized control trial (Magits et al., 2023).

The LUISTER training program yielded significant improvements in outcomes provided during the trial (based on the monitoring tests: DTT and phoneme identification in quiet). Training also improved speech understanding in noise (based on a sentence in noise test) and health-related quality of life (based on a quality-of-life questionnaire; NICQ). The magnitude of training-induced transfer to speech in noise understanding was greater than 2 dB for half of the participants. Moreover, adherence to the program was very high, as was the (technical) usability (median 91, IQR=5°).

At the end of the study trial, participants rated the usefulness of the LUISTER program on a Likert scale: 77% reported to find the training useful (= 4 or 5 on the Likert scale) and 88% of the participants would recommend the program to someone else. During the use of the LUISTER training tasks, no adverse events were reported, which indicates the software is safe to use in our participants.

##### mHealth for AR

ALICE is not the first programme to deliver AR to clients by using mHealth. Different apps or websites are already available on the market (Olson 2015, 2018) (e.g. [www.clearworks4ears.com](http://www.clearworks4ears.com); [www.cogmed.com](http://www.cogmed.com); [www.laceauditorytraining.com](http://www.laceauditorytraining.com)). These apps or websites deliver AR to the client in different languages (mostly English) and offer different types of exercises. Interestingly, none have a CE-mark and none have been evaluated as an app. Part of these materials have been researched in different studies but results of these studies show a high degree of variability in outcome.

Little evidence is available on auditory training improving outcomes for persons with HI. A very comprehensive systematic review on the efficacy of computerized auditory training for persons with HI by Henshaw and Ferguson (2013) is cautiously positive. However, the authors identified several scientific, methodological, and study quality issues that preclude solid conclusions and highlight the need for higher-level evidence.

#### 3.5.3.2. Evaluation of clinical data relevant to the proposed clinical investigation

To date, no consensus exists on how effectiveness of AR should be assessed and a comparison across apps is impossible due to differences between languages. In the current study, a validated measure for speech understanding in noise is used as the main outcome, complemented with non-auditory outcomes to evaluate effectiveness in a broader context of functioning and participation.

Justification for the chosen materials:

- *A speech in noise test* (Dutch: LIST sentences or BLU words, French: Lafon's dissyllabic words) will evaluate the persons' ability to perceive speech in noise, in a clinically controlled condition.

Speech in noise understanding has been reported as the number one difficulty that persons with HI encounter in daily life.

We should keep in mind that sentence testing in noise only partly resembles real-life listening difficulties (well-articulated sentences in speech-weighted noise, whereas in real life, speech understanding is also influenced by high paced speech, interruptions by other talkers, and other acoustical factors such as background noise, reverberation, and cognitive factors). However, it is not possible to account for all real-life factors in a testing environment.

- Besides the clinically validated measures we will evaluate the daily life listening with *questionnaires* that tap into the listeners' daily life experience:
  - o We will evaluate perceived listening difficulties with the Speech Spatial and Quality of hearing questionnaire (SSQ12) which evaluates typical listening situations and is commonly used in clinical practice and the Client Oriented Scale of Improvement (COSI) which evaluates an individual's listening difficulties reported by the listener over time.
  - o We will also evaluate the benefit of AR with non-auditory outcomes to gain insight in how listening difficulties are perceived and experienced by the listener and how it influences their participation and functioning in society. We will use the effort assessment scale (EAS) which evaluates the amount of effort needed by an individual and the communication and acceptance scale (CAS) which measures clinical changes in "communication strategies and the emotional consequences, knowledge and acceptance of HI". Additionally we will use the International Outcome Inventory for Hearing Aids (IOI-HA) which evaluates the satisfaction of the clients with their hearing aids in daily life situations.

### 3.5.4. Benefits and risks of the investigational device and clinical investigation

#### 3.5.4.1. Anticipated clinical benefits

##### **FOR Experienced CI/HA users:**

We hypothesise that 75% of our subjects will:

- Indicate an enhancement in their daily life listening and/or communication strategies (primary)
  - o Enhanced speech understanding in difficult listening situations
  - o Reduced listening effort
- Indicate to be more knowledgeable about their HI and recognize the emotional consequences of their HI and (secondary)
- Indicate to be more satisfied with the delivered care and/or their hearing aid/cochlear implant in daily life (secondary).

##### **FOR first-time HA users:**

We hypothesise that 75% of our subjects will:

- Indicate an enhancement in their daily life listening and/or communication strategies (primary)
  - o Enhanced speech understanding in difficult listening situations
- Indicate to be more knowledgeable about their HI and recognize the emotional consequences of their HI and (secondary)

- Indicate to be more satisfied with the delivered care and/or their hearing aid in daily life (secondary)
- Indicate to habituate faster to their hearing aids (secondary).

### 3.5.4.2. Residual risks associated with the investigational device, as identified in the risk analysis report

(See Risk analysis in IB). In summary, only 1 risk remains significant after implementation of the control measures. The occurrence of (small) software failures remains high, but the severity of the harm is in our case considered to be minimal as the device is used as an additional service on top of the standard of care. As the risks are associated with negligible potential harms, we consider the harm and the risk as acceptable, and we can, with certainty, say that the benefits of the app (as already demonstrated in section 3 of the IB) outweigh these minimal risks.

### 3.5.4.3. Risks associated with participation in the clinical investigation and mitigations

See Safety section (3.5.14).

## 3.5.5. Objectives and hypotheses of the clinical investigation

### 3.5.5.1. The purpose of the clinical investigation, claims for clinical performance or effectiveness and safety of the investigational device that are to be verified

#### Claims

##### ALICE-Client

- **Enhancement** - the app enhances daily life listening and the ability to manage difficult listening situations

##### ALICE-pro

- **Data-driven hearing care** – the HCP will be able to deliver an additional rehabilitation service, that will be evidenced-based and data-driven and it will enforce valued based hearing care.

#### Hypotheses on the clinical performance & effectiveness of the ALICE app

##### User-oriented outcomes for experienced HA/CI users

After 8 weeks of continued use of the ALICE-Client app persons with HI will:

- Indicate enhancement in their daily life listening and/or communication strategies (primary)
  - Enhanced speech understanding in difficult listening situations
  - Reduced listening effort
- Indicate to be more knowledgeable about their HI and recognize the emotional consequences of their HI (secondary)
- Indicate to be more satisfied with the delivered care and/or their hearing aid/cochlear implant in daily life (secondary).

##### User-oriented outcomes for persons in their hearing aid trial (first time HA users):

- Indicate an enhancement in their daily life listening and/or communication strategies (primary)
  - Enhanced speech understanding in difficult listening situations
- Indicate to be more knowledgeable about their HI and recognize the emotional consequences of their HI and (secondary)

- Indicate to be more satisfied with the delivered care and/or their hearing aid in daily life (secondary)
- Indicate to habituate faster to their hearing aids (secondary).

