### 3.5.6.3. Research ARM 2 (approved by EC on 20/02/2023 – ref. CIV-22-06-039801)

The main goal of the second arm of the clinical study is to evaluate the performance (and viability) of the ALICE app in a specific part of the hearing care path, i.e. during the first 4 to 8 weeks of hearing aid adoption, commonly referred to as the 'hearing aid trial period'. This period is mandatory before purchasing a hearing aid.

The hearing aid trial period starts once the client has chosen a suitable hearing aid together with his or her HCP. It is therefore not possible to create a waiting list for enrolled participants. For this reason we will facilitate a rolling start with eligible participants during 9 consecutive months in 6 hearing aid centers geographically spread across Flanders, Belgium.

As the enrolment rate of this arm is expected to be lower than in the first research arm, the duration of the study will be longer. The duration of the study is estimated between 10 and 12 months (see procedures for the overview of the time line).

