### Primary and secondary endpoints, with rationale for their selection and measurement

The outcome measures that will be used as an endpoint to determine the clinical benefit of the ALICE app are:

- Clients - Effectiveness of the app is ensured
  - Enhanced outcome measures at the end of the hearing aid trial period (Primary)
    - Enhanced speech understanding in noise
    - Enhanced speech understanding in daily life
  - Increased knowledge of the consequences of HI (Secondary)
  - Increased satisfaction of care delivery (Secondary)
  - Increased habituation to hearing aids (Secondary)
    - Satisfaction with hearing aid
    - Duration of daily hearing aid use
- HCP - Effectiveness of the app is ensured
  - Enhanced care delivery (Secondary)
    - Reduced F2F time with HCP (reduction in time, appointments, hearing aid fittings, tests, ...)

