#### *Recruitment of clients*

- Local IPs will be responsible for the recruitment of patients. Before they start with recruiting they will be instructed with clear inclusion and exclusion criteria (see 3.5.6.3 Subjects)
- The number of clients that should be enrolled will be in the range of 20-30 for every investigator site
- To be able to recruit 120 first time hearing aid users, the recruitment period will be spread out from April 2023 to August 2024, employing a rolling start strategy.
- Enrolment of clients
- Clients who match the criteria, will receive a brief introduction about the study, which may or may not include the ALICE app. If they are interested to participate in the study, they will receive an information brochure about the study programme, in which a more detailed description is provided (details about the course of the study, the 3 visits, the duration of the study and their rights and responsibilities.) They will also be informed that they will be assigned randomly to one of the two groups.
- If clients agree to participate in the study they will sign an informed consent form.
- After being stratified by age clients will be randomly assigned to one of the two groups by a KU Leuven researcher using an automatic seed generator:
  - 1 group will receive the standard of care
  - 1 group will receive the standard of care with additional support of ALICE app

	Responsible	Accountable
Clients match the criteria	Local PI	KUL PI

Clients get a brief introduction about the app and the goals of the study; when interested they receive a detailed information brochure	Local PI	
Clients sign an Informed Consent	Local PI	KUL PI
Clients are enrolled in the study	Local PI	KUL PI
Allocation of groups and randomization	Local PI	KUL PI

*The study program and test protocol*

- Onboarding procedure: once the clients are enrolled they will receive a standard onboarding procedure, which will be led by the local PI. Within this procedure following points/formalities will be discussed with their client:
  - The study programme/course of the study
  - Appointment schedule to perform the tests
  - Procedure to follow in case of change
  - Contact information in case of questions
  - Risk & Safety management (see safety section), with special attention to following procedures:
    - Procedure to control the loudness of the stimuli provided by the app
    - Procedure to follow to ensure safe data management (compliant with GDPR)

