    - Procedure to follow in case of adverse events and/or device malfunction
  - Rights and responsibilities
- Installation of the app
  - Intended use of the app
  - Compatibility of the app with personal (streaming) devices,
  - Instruction to use the app
  - First installation and set-up of account
- Test protocol (see below and Fig. 4)

*Description of all the clinical-investigation-related procedures that subjects undergo during the clinical investigation including any deviation from normal clinical practice*

Below, the timeline of the test protocol is presented after allocation to a treatment group a client will be assessed with speech in noise and questionnaires (Figure 5). Followed by 4 to 6 weeks use of the ALICE app. The same outcome measures will be assessed at the end of the hearing aid trial period to evaluate the benefit of the intervention.

[figure not shown]

Figure 5. Timeline of the test protocol of the second research arm

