#### 3.5.7.2. Statistical analysis

Statistical analyses will be performed using either the R programming language and statistical environment (R Core Team, 2017) or IBM SPSS 27. Potential missing data will be replaced using multiple imputation (in SPSS).

Data for hearing aid users and cochlear implant users will be analysed separately. Potential relations between outcomes will be determined in a within-subject design, i.e., baseline session outcomes will be compared to the final session outcomes, with a repeated measures ANOVA ( $\alpha = 0.05$ ). We will correct for multiple comparisons using Dunn post-hoc tests with Holm correction (Dunn, 1961).

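### Arm 2 hypothesises faster habituation but compares an end-of-trial level with baseline, and it has no outcome or handling rule for hearing aids that are returned

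*Combined protocol and SAP*

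**What the plan says.** The speed claim appears twice, under first-time hearing-aid users in section 3.5.4.1 and in the Arm 2 hypotheses of section 3.5.5.1: "Indicate to habituate faster to their hearing aids (secondary".

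The Arm 2 endpoint list in section 3.5.6.3 words it differently: "Increased habituation to hearing aids (Secondary". Its two components are "Satisfaction with hearing aid" and "Duration of daily hearing aid use". Table 2 measures use of the aid with the IOI-HA and a datalog, and gives no read-out times.

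On timing, the Arm 2 procedures describe an assessment after allocation and then: "The same outcome measures will be assessed at the end of the hearing aid trial period to evaluate the benefit of the intervention". The enrolment text refers to "the 3 visits, the duration of the study and their rights and responsibilities". Section 3.5.7.2 states one contrast, baseline session against final session.

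On keeping the aid, the introduction to section 3.5.6.3 says of the hearing-aid trial: "This period is mandatory before purchasing a hearing aid". The Arm 1 inclusion criteria (3.5.6.2) require hearing-aid clients to have finished that trial and decided to buy. The Arm 2 criteria contain no such condition. Tables 2 and 3 and the Arm 2 endpoint list include neither purchase nor return of the aid. The only rule for missing values, in section 3.5.7.2, is: "Potential missing data will be replaced using multiple imputation (in SPSS".

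**The concern.** There are two separate gaps.

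**Speed against level.** Faster habituation means reaching a given level of use or comfort sooner. The plan defines no threshold, no time-to-habituation variable and no analysis of an intermediate reading. For a first-time user, daily use at baseline is presumably zero or undefined, so for that component the planned contrast amounts to comparing end readings. If both groups approach the same plateau by the end of the trial, a real gain in speed shrinks and may be read as no effect. Conversely, a higher end level would be reported as faster habituation when it may be only a higher plateau.

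**Returned aids.** A client who gives the aid back during the trial may have no end-of-trial daily use. If that value is treated as missing, the general imputation rule fills it with a positive number of hours for someone who no longer has an aid. Section 3.5.1.3 argues that added rehabilitation services could raise adherence and uptake. A benefit of that kind, fewer aids given up, could then disappear from the use outcome and would not be recorded anywhere else.

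**Working it through.** The plan gives no figure for habituation, so there is none to reproduce. The calculations below are illustrations, and their inputs are assumptions unless a source is named.

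**1. How much of a speed difference an end reading keeps**

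Assume daily use builds towards the same plateau in both groups: share of plateau at week t = 1 − exp(−t/τ), with a smaller τ meaning faster. The end times come from the plan: a hearing-aid trial of 4 to 8 weeks (introduction to 3.5.6.3), app use for 4 to 6 weeks (Arm 2 procedures) and an 8-week training period (Arm 2 bias measures).

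| Week | τ = 1 | τ = 2 | Gap (points), 1 v 2 | τ = 4 | Gap (points), 2 v 4 |
|---|---|---|---|---|---|
| 2 | 86.5% | 63.2% | 23 | 39.3% | 24 |
| 4 | 98.2% | 86.5% | 12 | 63.2% | 23 |
| 6 | 99.8% | 95.0% | 5 | 77.7% | 17 |
| 8 | 99.97% | 98.2% | 2 | 86.5% | 12 |

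With quick habituation (1 v 2 weeks) the end reading keeps about half of the week-2 gap at week 4 and little of it at week 8. With slow habituation (2 v 4 weeks) it keeps most of the gap at week 6. The loss depends on unknown curves and on which of the stated durations applies.

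These are values at a point in time. A datalog may instead report an average since fitting, which is 1 − (τ/T)(1 − exp(−T/τ)) over T weeks. For T = 6:

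- τ = 1: 1 − (1/6)(0.9975) = 83.4%
- τ = 2: 1 − (2/6)(0.9502) = 68.3%, a gap of 15 points from τ = 1

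Such an average keeps more of the speed signal, but it cannot tell quicker build-up from a higher plateau. The plan does not say which form is recorded.

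The same formula for a first interval ending at week 2 (an assumed date for the middle visit):

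- τ = 1: 1 − (1/2)(0.8647) = 56.8%
- τ = 2: 1 − (2/2)(0.6321) = 36.8%, a gap of 20 points from τ = 1
- τ = 4: 1 − (4/2)(0.3935) = 21.3%, a gap of 15 points from τ = 2

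An early interval reported beside a separate end level lets the reader see whether a gap opens early and then closes.

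**2. What imputation does to returned aids**

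Assume return rates of 10% (app) and 20% (control), 8 h/day among keepers in both groups, and 0 h/day after return.

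- All randomised clients: 0.90 × 8 − 0.80 × 8 = 7.2 − 6.4 = 0.8 h/day in favour of the app.
- Returners imputed from keepers: 8 − 8 = 0 h/day.
- Range: the hidden difference is 8 × (difference in return rates), so 0.4 h/day for 5 points and 1.6 h/day for 20 points. If return rates are equal it is 0.

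**3. Keepers only**

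If returners are the lowest users of a normally distributed measure, the mean among keepers is raised by φ(z)/(1 − p), where p is the return rate and z its normal quantile.

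- p = 10%: 0.1755/0.90 = 0.195 SD
- p = 20%: 0.2800/0.80 = 0.350 SD

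A keepers-only comparison would therefore move by 0.195 − 0.350 = −0.155 SD against the app with no true difference in use. It can be a sensitivity analysis but not the main one.

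**The case against.** The strongest reply is that this is one unpowered secondary outcome, and that a higher level at a fixed point in a short window is a fair proxy for speed. That stands in part: with time constants of 2 v 4 weeks, most of the gap survives to week 6. It does not remove the mismatch, because the proxy is only good if habituation is slow relative to the trial and the plateaus are equal. The plan states neither.

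Several stronger readings are tempting and are not supported.

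- A reader might infer that habituation is read only at the end. The text describes baseline and end assessments and analyses only those, but Arm 2 has three visits, the Figure 5 timeline is not reproduced and datalog read-out times are not given. An interim read-out may exist. The gap is that no stated analysis uses one.
- A reader might infer that clients who return the aid have no value. The documents are silent. A client who declines at the end of the trial can still have a full datalog and questionnaire, so the problem arises only where return leaves the value missing.
- A reader might infer that failed habituation goes unmeasured. Low logged use or low satisfaction would show it in part among clients who are assessed.
- A reader might take the 20–40% adoption figure in section 3.5.1.3 as a guide to returns. It concerns uptake among people who seek help, whereas Arm 2 clients have already chosen an aid. It is not a return rate.

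It is also fair to say that section 3.5.7.2 names no imputation model, so drawing from keepers is an assumption, and that zero use after return is one choice of estimand among several. Because the plan states no choice, the generic rule applies by default.

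**Conclusion.** The point holds in a limited form. The hypothesis is about speed, the endpoint is a level, and baseline against final session is the only stated contrast. As written, the analysis can support a claim of greater habituation at the end of the trial but not of faster habituation. The size of the loss cannot be fixed from the documents: under the assumed curves, an end reading at week 6 keeps between 5 of 23 points and 17 of 24.

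Separately, return of the aid is possible in Arm 2, is not an outcome, and is covered only by generic multiple imputation. If returns leave use missing and are imputed from keepers, a benefit made up of fewer returns is hidden, by 0.8 h/day under the assumed 10% v 20% and 8 h/day. If return rates are equal or values are obtained at return, the effect is small or nil.

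The changes should be made, since they are cheap and settle what may be claimed. They concern a secondary outcome and do not by themselves call the primary speech-understanding comparison into question.

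**What to change.** 1. In the Arm 2 endpoint list, Table 2 and section 3.5.7.2, name datalog daily use in the first inter-visit interval as the early-habituation outcome, compared between groups. Keep end-of-trial use as a separate level outcome. State the read-out times and whether each value is an average over the interval. If this is not wanted, change 'faster' to 'greater' in sections 3.5.4.1 and 3.5.5.1.
2. Record kept or returned, with date, for every randomised Arm 2 client and report it by group. In the use analysis, count daily use after return as 0 instead of imputing it, with a keepers-only analysis as sensitivity. With 60 per group, power to separate 20% from 10% returns is only about 33%, so report the difference with its interval and do not make it a success criterion.
3. Reconcile the durations given for Arm 2 (4 to 8 weeks, 4 to 6 weeks and 8 weeks), because they set when the end reading is taken.

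Cost: one datalog read-out at a visit that already takes place (if not already planned), an eCRF entry for kept or returned with its date, and a few sentences of text. No extra visits or clients are needed. The downsides are that use data become more skewed by zeros, and that early-interval use still partly mixes speed with level. The text does not give the date of the middle visit, which determines how early that interval is.
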